10.6.3 Breaking the Study Blind

There is no plan to break the study blind prior to the 3 month follow-up unless there is an SAE or as required by NIH or NYU IRB.

11 Source Documents and Access to Source Data/Documents

Source data is all information, original records of clinical findings, observations, or other activities in a clinical trial necessary for the reconstruction and evaluation of the trial. Source data are contained in source documents. Examples of these original documents, and data records include: hospital records, clinical and office charts, laboratory notes, memoranda, subjects' diaries or evaluation checklists, recorded data from automated instruments, copies or transcriptions certified after verification as being accurate and complete, and subject files. It is acceptable to use CRFs as source documents. If this is the case, it should be stated in this section what data will be collected on CRFs and what data will be collected from other sources.

The study case report form (CRF) is the primary data collection instrument for the study. All data requested on the CRF must be recorded. All missing data must be explained. If a space on the CRF is left blank because the procedure was not done or the question was not asked, write "N/D". If the item is

CONFIDENTIAL

This material is the property of the NYU School of Medicine and Langone Medical Center. Do not disclose or use except as authorized in writing by the study sponsor
Interventional Template Version: 11 January 2019

not applicable to the individual case, write "N/A". All entries should be printed legibly in black or blue ink. If any entry error has been made, to correct such an error, draw a single straight line through the incorrect entry and enter the correct data above it. All such changes must be initialed and dated. DO NOT ERASE OR WHITE OUT ERRORS. For clarification of illegible or uncertain entries, print the clarification above the item, then initial and date it.

Access to study records will be limited to IRB-approved members of the study team. The investigator will permit study-related monitoring, audits, and inspections by the IRB, the sponsor, government regulatory bodies, and University compliance and quality assurance groups of all study related documents (e.g. source documents, regulatory documents, data collection instruments, study data etc.). The investigator will ensure the capability for inspections of applicable study-related facilities.

Participation as an investigator in this study implies acceptance of potential inspection by government regulatory authorities and applicable University compliance and quality assurance offices.

12 Quality Assurance and Quality Control

QC procedures will be implemented beginning with the data entry system and data QC checks that will be run on the database will be generated. Any missing data or data anomalies will be communicated to the site(s) for clarification/resolution.

Following written SOPs, the monitors will verify that the clinical trial is conducted and data are generated, documented (recorded), and reported in compliance with the protocol, GCP, and the applicable NYU IRB regulatory requirements.

The investigational site will provide direct access to all trial related sites, source data/documents, and reports for the purpose of monitoring and auditing by the sponsor, and inspection by local and regulatory authorities.

13 Ethics/Protection of Human Subjects

13.1 Ethical Standard

The investigator will ensure that this study is conducted in full conformity with Regulations for the Protection of Human Subjects of Research codified in 45 CFR Part 46, 21 CFR Part 50, 21 CFR Part 56, and/or the ICH E6.

13.2 Institutional Review Board

The protocol, informed consent form(s), recruitment materials, and all participant materials will be submitted to the IRB for review and approval. Approval of both the protocol and the consent form must be obtained before any participant is enrolled. Any amendment to the protocol will require review and approval by the IRB before the changes are implemented to the study. All changes to the consent form will be IRB approved; a determination will be made regarding whether previously consented participants need to be re-consented.

13.3 Informed Consent Process

13.3.1 Consent and Other Informational Documents Provided to Participants

Consent forms describing in detail the study device, study procedures, and risks are given to the participant and written documentation of informed consent is required prior to starting intervention/administering study product. The following consent materials are submitted with this protocol: informed consent form.

CONFIDENTIAL

This material is the property of the NYU School of Medicine and Langone Medical Center. Do not disclose or use except as authorized in writing by the study sponsor
Interventional Template Version: 11 January 2019

13.3.2 Consent Procedures and Documentation

Informed consent is a process that is initiated prior to the individual's agreeing to participate in the study and continues throughout the individual's study participation. Extensive discussion of risks and possible benefits of participation will be provided to the participants and their families. Consent forms will be IRB-approved and the participant will be asked to read and review the document. The investigator will explain the research study to the participant and answer any questions that may arise. All participants will receive a verbal explanation in terms suited to their comprehension of the purposes, procedures, and potential risks of the study and of their rights as research participants. Participants will have the opportunity to carefully review the written consent form and ask questions prior to signing. The participants should have the opportunity to discuss the study with their relatives or think about it prior to agreeing to participate. The participant will sign the informed consent document prior to any procedures being done specifically for the study. The participants may withdraw consent at any time throughout the course of the trial. A copy of the signed informed consent document will be given to the participants for their records. The rights and welfare of the participants will be protected by emphasizing to them that the quality of their medical care will not be adversely affected if they decline to participate in this study.

Subjects will be emailed a PDF version of the protocol and the phone number of a study team member to call after they have reviewed the consent. The study team member will then explain the consent to the subject, and ask if the subject has any questions. If the subject agrees to participate, they will electronically sign the informed consent document and email it back to the study team. The consent process, including the name of the individual obtaining consent, will be thoroughly documented in the subject's research record.

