6.1.3 Device Programming

To ensure blinding, devices will be pre-programmed in advance by an independent staff member, who will not take part in the treatment and assessment¹¹⁸⁻¹²⁰.

For active tDCS, the device is programmed to ramp up to 2.0 mA (for 30 seconds), provide constant current throughout session (19 minutes), and then ramp down (for 30 seconds) at the end.

For sham tDCS, the device is programmed to ramp up to 2.0 mA (for 30 seconds) followed by a ramp down (30 seconds), with no current delivery for 18 minutes, and then ramp up (for 30 seconds) and down (for 30 seconds) at the end.

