While the remote connection does allow for a participant to provide a sample that is not their own to test, we believe that this occurrence would be of very low likelihood in this study sample. The participants are enrolled based on disclosed cannabis use, they are not incentivized in any way to decrease their cannabis use, and there would be no other primary or secondary gain for invalidating this procedure. Alternatively, in the similarly unlikely event that participants have falsely reported cannabis use and test negative at baseline, they will be withdrawn.

- Participants will complete self-report questionnaires about their physical and mental health, and cannabis use through REDCap survey function (see assessments section 8.2 below).
- For exploratory research, participants will complete cognitive measures (BICAMS, Cogstate Brief Battery) and MS symptom questionnaires.
- Participants will have their first 20-minute tDCS session of either 2.0mA active or sham tDCS combined with mindfulness meditation. At each treatment session, participants will complete brief adverse event reports before and after each session. Once the study technician visually confirms correct headset placement and participants confirms adequate contact quality (moderate or good), the technician will provide the participant with a one-time use unlock code to enter into their tDCS device. The participant enters the code when ready to initiate the stimulation. During each stimulation session participants will listen to a guided mindfulness meditation audio track on the study provided laptop computer.
- Remotely-Supervised tDCS Sessions 2-20:
 - Over the next 4-6 weeks, participants will complete the remaining daily tDCS + mindfulness meditations as described above for session 1.
 - After sessions 5, 10, and 15 participants will complete self-report questionnaires using REDCap survey function.
 - tDCS session 20 & Treatment-end: After completing the final tDCS session participants will repeat the baseline self-report questionnaires and measures, and the single panel cannabis test. Participants will be asked to return the equipment via Fedex using a prepaid return label.
- Post treatment-end follow-ups

CONFIDENTIAL

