10.6 Measures to Minimize Bias

10.6.1 Enrollment/Randomization/Masking Procedures

In this pilot RCT, participants will be randomized 2:1 into one of two intervention groups consisting of active (Group 1) vs. sham (Group 2) tDCS paired with mindfulness meditation practice. A study team member who otherwise will not be involved in administering research procedures will randomize the device and keep the assignments in confidentiality (e.g. password protected spreadsheet).

During a sham session, the device is programmed to ramp up to the desired intensity (2.0 mA) and ramp down for the initial 60 seconds, with no current delivery during the session aside from the 60 seconds in the beginning and then again at the end of the session. These brief periods of stimulation serve to mimic the effects of a true stimulation session.

Randomization: We will stratify randomization by years of cannabis use (4 years or less vs. 5 or more years). Urn randomization will be used to balance the randomization assignment with respect to these strata. The purpose of stratification is to distribute this potential prognostic factor equally across treatment groups.

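### Section 13.3.2 has subjects emailed the protocol rather than the consent form; followed as written, this would disclose the sham time profile and could weaken the blind

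*Combined protocol and SAP*

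**What the plan says.** On what is sent at consent, Section 13.3.2 states: "Subjects will be emailed a PDF version of the protocol and the phone number of a study team member to call". The sentence then ties that call to the subject having reviewed the consent. A team member explains the consent, and the subject signs the consent document electronically and emails it back.

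Section 13.3.1 states: "The following consent materials are submitted with this protocol: informed consent form". Section 13.5 places the study protocol among the items to be held in strict confidence. The page footers bar disclosure unless the sponsor authorizes it in writing.

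On what the protocol contains, Section 6.1.3 gives both waveforms, and the Protocol Summary repeats them. A sham session opens by rising to 2.0 mA and falling back, half a minute each way; the description then runs "with no current delivery for 18 minutes, and then ramp up (for 30 seconds) and down (for 30 seconds) at the end". For active, after a 30-second ramp up, the device is to "provide constant current throughout session (19 minutes), and then ramp down (for 30 seconds) at the end". Section 10.6.1 restates the sham profile ("with no current delivery during the session aside from the 60 seconds in the beginning and then again at the end of the session") and gives its purpose: "These brief periods of stimulation serve to mimic the effects of a true stimulation session". No redacted or participant version of the protocol is mentioned.

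**The concern.** The sham condition is built so that a participant feels something at the start and end of each session and cannot tell what happens in between. A participant who has read the waveform description knows what to look for. The consent procedure, read literally, supplies that description before randomization.

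This matters because the primary measures in Section 4.2.1 (K10, PANAS, TLFB, MCQ-17, DFAQ-CU, CWS) are all reported by the participant. If beliefs about allocation come to differ between arms, expectancy can shift these answers, most plausibly in favour of active stimulation. Section 10.4.2 says the pilot is meant to yield effect sizes for a later grant application, so any such bias would carry into the planning of the next trial.

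**Working it through.** No sample size, power or alpha formula applies. The check is which document is meant, what it would disclose, and whether the plan would notice a loss of masking.

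**1. Which document is sent?**

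- *Protocol:* the operative words of 13.3.2.
- *Consent form:* the rest of that sentence and the steps after it; 13.3.1, which lists nothing else; and Section 5.5, which gives the participant as long as she needs to review the consent form and mentions no protocol review.
- *Against release of the protocol:* Section 13.5 and the footers, unless the sponsor has authorized release in writing. The documents record no such authorization.

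The passages do not agree. The weight of context favours the consent form, but the explicit instruction names the protocol.

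**2. What would the protocol disclose?** Adding the segments in Section 6.1.3:

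- Sham: 30 + 30 + (18 × 60) + 30 + 30 = 1,200 s = 20 min.
- Active: 30 + (19 × 60) + 30 = 1,200 s = 20 min.

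Both reproduce the stated 20-minute session. Sham has current for 30 + 30 + 30 + 30 = 120 s, that is 2 of 20 minutes (10%). Active has current for all 20. Section 10.6.1 agrees with Section 6.1.3.

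On the session clock, the arms differ in two ways that a reader could try to check:

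- From minute 1 to minute 19, active is at constant current and sham has none.
- At minute 19, sham starts a new ramp up. Active has none and only ramps down, from 19.5 minutes.

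**3. Is there anything to feel?** Section 2.4.1 names warming, itching and tingling under the electrodes as the most common side effects and describes side effects as mild and transient. Section 8.1 has a 90-second tolerability test at 2.0 mA before session 1. It would give a felt reference if it delivers the same current in both arms, which the text does not say. The documents give no data on whether current in the middle 18 minutes is perceptible.

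**4. Would the plan notice?** The blinding questionnaire is given at the 3-month follow-up (Sections 8.1 and 8.3.6). The primary endpoints are change from baseline to treatment end (Section 4.2.1). Masking lost during treatment would be recorded only about three months after the primary data were collected. The one objective measure, the urine strip, is a yes/no test used as secondary confirmation of the TLFB (Section 8.2.2).

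**The case against.** The strongest answer is that nobody intends to send the protocol. Everything around the sentence concerns the consent form, and a document marked confidential on its pages is an unlikely handout. That reading is plausible and may well be correct. It lowers the likelihood of harm but does not remove the need for a correction: the sentence is an operative instruction, staff who comply with it would disclose the sham profile, and the same edit resolves a slip.

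A second answer is that disclosure is not the same as unblinding. This stands. A reader might infer that participants are being told how to recognise their arm. The documents do not support that: the protocol gives timings and no guidance on guessing, sensations described as transient may also fade under active stimulation, and perceptibility is not reported. For the same reason, any bias stated in standard deviations would rest wholly on assumed values.

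A reader might also count other disclosed details, such as the K10 entry range or the handling of a negative baseline urine test, as part of the problem. Neither says anything about allocation, and the K10 is already given at phone pre-screening, before consent (Section 8.3.1).

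Finally, the plan does assess blinding, by guess, reason and confidence (Section 10.6.2). That is a partial safeguard, limited by its timing.

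**Conclusion.** The point holds as an inconsistency with a credible consequence. Section 13.3.2 conflicts with 13.3.1, 13.5 and the footers. If followed literally, it would give the sham and active time profiles to everyone taken through consent, including the approximately 52 who sign (Section 5.6). Not all of these would go on to 20 sessions, since 42 evaluable participants are expected.

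That such disclosure could weaken the blind rests on two assumptions that the documents neither confirm nor exclude: that participants read the relevant sections, and that they can feel a difference between minutes 1 and 19 or at the late ramp. No magnitude can be derived. The case for acting is that the instruction is wrong on its face or at least ambiguous, the outcomes are self-reported, and the correction is simple.

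**What to change.** In Section 13.3.2, change the emailed item from a PDF of the protocol to a PDF of the IRB-approved informed consent form. Add one sentence saying that the protocol and device programming details are not given to a participant until her 3-month outcome data and blinding questionnaire are complete. This matches the point at which Section 8.3.6 already unblinds her, and it brings 13.3.2 into line with 13.3.1 and 13.5.

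The cost is a short wording amendment with IRB review; visits, procedures, sample size and analysis do not change. The consent form was not available for this review, so whether it describes the sham timing is a separate question that this edit does not settle.

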13.3.2.1 Capacity to Consent

Based on [name] clinical practice and research, our study population is not expected to have significant cognitive impairment. Subject capacity to provide informed consent will be determined by trained team members or PI who will ask the participant open-ended questions regarding their understanding of key research information. All team members will be trained in GCP-ICH guidelines and will receive additional training by the PI or an experienced study team member. Reading comprehension will be assessed using the WRAT-4 and participants must score ≥ 85 . A licensed clinician will not be required to ask the questions below or administer the WRAT-4 which has normative values.

Questions will include:

- In your own words, can you please explain the purpose of this research?
- What does it mean that your participation is voluntary?
- What happens if you sign consent and then later change your mind?
- What are the risks and benefits of participating in this study?

Reasonable judgement may be used to determine whether a participant's responses reflect proper understanding of key research procedures. Patients who do not answer these questions adequately will be excluded from the study. Continued capacity assessments are not required as cognitive decline associated with MS progresses over years so we don't expect any subjects will lose capacity over the course of 4.5 months.

13.4 Posting of Clinical Trial Consent Form

N/A

13.5 Participant and Data Confidentiality

Information about study subjects will be kept confidential and managed according to the requirements of the Health Insurance Portability and Accountability Act of 1996 (HIPAA). Those regulations require a signed subject authorization informing the subject of the following:

CONFIDENTIAL

This material is the property of the NYU School of Medicine and Langone Medical Center. Do not disclose or use except as authorized in writing by the study sponsor
Interventional Template Version: 11 January 2019

- What protected health information (PHI) will be collected from subjects in this study
- Who will have access to that information and why
- Who will use or disclose that information
- The rights of a research subject to revoke their authorization for use of their PHI.

In the event that a subject revokes authorization to collect or use PHI, the investigator, by regulation, retains the ability to use all information collected prior to the revocation of subject authorization. For subjects that have revoked authorization to collect or use PHI, attempts should be made to obtain permission to collect at least vital status (i.e. that the subject is alive) at the end of their scheduled study period.

Participant confidentiality is strictly held in trust by the participating investigators, their staff, and the sponsor(s) and their agents. Therefore, the study protocol, documentation, data, and all other information generated will be held in strict confidence. No information concerning the study or the data will be released to any unauthorized third party without prior written approval of the sponsor.

The study monitor, other authorized representatives of the sponsor, representatives of the IRB or pharmaceutical company supplying study product may inspect all documents and records required to be maintained by the investigator, including but not limited to, medical records (office, clinic, or hospital) and pharmacy records for the participants in this study. The clinical study site will permit access to such records.

The study participant's contact information will be securely stored at each clinical site for internal use during the study. At the end of the study, all records will continue to be kept in a secure location for as long a period as dictated by local IRB and Institutional regulations.

Study participant research data, which is for purposes of statistical analysis and scientific reporting, will be transmitted to and stored at NYU Langone Medical Center. This will not include the participant's contact or identifying information. Rather, individual participants and their research data will be identified by a unique study identification number. The study data entry and study management systems used by clinical sites and by NYU Langone Medical Center research staff will be secured and password protected. At the end of the study, all study databases will be de-identified and archived at the NYU Langone Medical Center.

To further protect the privacy of study participants, a Certificate of Confidentiality will be obtained from the NIH. This certificate protects identifiable research information from forced disclosure. It allows the investigator and others who have access to research records to refuse to disclose identifying information on research participation in any civil, criminal, administrative, legislative, or other proceeding, whether at the federal, state, or local level. By protecting researchers and institutions from being compelled to disclose information that would identify research participants, Certificates of Confidentiality help achieve the research objectives and promote participation in studies by helping assure confidentiality and privacy to participants.

